8.1.1 Instructions for rapid notification of Serious Adverse Events

Reporting responsibility

For all studies for which Seattle Genetics has provided Product:

- **Reporting Timeframe:** The Principal Investigator (Stanford) will report to Seattle Genetics Drug Safety by facsimile any Serious Adverse Event (SAE) that occurs in a study subject within 24 hours of first awareness of the event. The Co-Principal Investigator from the sub-site will report any SAEs to the main site (Stanford) within 24 hours by facsimile or by email to [contact] and these will be submitted to Seattle Genetics Drug Safety by Principal Investigator.
- **Reporting Forms:** The Principal Investigator and Co-Principal Investigator will report such SAEs using the Seattle Genetics SAE Report Form or the approved local regulatory form (ie, FDA MedWatch form, CIOMS, etc.) *to include an assessment of causality to the Product*. SAEs should be reported as soon as they are determined to meet the definition, even if complete information is not yet available.

A study of brentuximab vedotin (SGN-35) in CD30-positive systemic mastocytosis with or without an associated hematological clonal non-mast cell lineage disease (AHNMD)

- **Reporting Period:** The reportable events that are subject to this provision are those that occur from the start of administration of the first dose of the Product through thirty (30) days after discontinuation of the Product. SAEs occurring more than thirty (30) days after discontinuation of the Product that are assessed by the Investigator as related to the Product should also be reported.
- **Follow-up Information:** The Principal Investigator will assist Seattle Genetics in investigating any SAE and will provide any follow-up information reasonably requested by Seattle Genetics.
- **Regulatory Reporting:** Reporting an SAE to Seattle Genetics does not relieve the Principal Investigator conducting the study of the responsibility for reporting it to the FDA, local regulatory authority, or IRB/IEC as required.

Sponsor Responsibilities

As the sponsor of the study, the Principal Investigator and/or Institution must ensure that the study is conducted in accordance with the provisions of the ICH GCP Guidelines and all applicable local and regulatory requirements. The Principle Investigator must assume all regulatory responsibilities including, but not limited to, IRB/IEC approvals, regulatory approvals, monitoring responsibilities and any and all reporting obligations to local regulatory Authorities.

EC/IRB Notification by Investigator

Reports of all serious adverse events (including follow-up information) must be submitted to the EC/IRB in accordance with the institutional policy. Copies of each report and documentation of EC/IRB notification and receipt will be kept in the Study binder.

8.1.2 Instructions for rapid notification of pregnancies

Each pregnancy that started during the study must be reported by the investigator to Seattle Genetics within 24 hours of learning of its occurrence. Pregnancies and pregnancy follow-up should be reported on the Clinical Trial Pregnancy Form but any serious adverse event experienced during pregnancy must be reported on the FDA Form 3500 and Serious Adverse Event Report Form. Pregnancy follow-up should describe the outcome of the pregnancy, including any voluntary or spontaneous termination, details of the birth, the presence or absence of any congenital abnormalities, birth defects, maternal or newborn complications and their relation to the Seattle Genetics study drug (or therapy).

8.2 Administrative procedures

8.2.1 Changes to the protocol

Study Initiation

As the sponsor of the study, the Principal Investigator and/or Institution must provide the following to Seattle Genetics prior to initiation of Seattle Genetics support (provision of Product):

- Final study protocol

A study of brentuximab vedotin (SGN-35) in CD30-positive systemic mastocytosis with or without an associated hematological clonal non-mast cell lineage disease (AHNMD)

- Fully executed IST Agreement
- Regulatory Response Documentation (IND or CTA documentation if applicable)
- IRB/IEC approval

Study Maintenance

Throughout the study, Seattle Genetics requires the following:

- At least one safety study status update per year, to include information on enrollment and study completion dates.
- Notification of any amendment to the original protocol after the research has begun; and *immediate* notification of any amendments made due to safety reasons.

Study Closure

Any Investigator and/or Institution conducting an IST is contractually required to provide Seattle Genetics with a written report of the final study results and a copy of the IND Annual Report (or equivalent in rest of world regions). Upon study closure, the Investigator and/or Institution will be required to certify that all safety reporting obligations were met.

8.2.2 Monitoring procedures

The Lead study investigator (Study Sponsor) is responsible for reviewing the protocol and case report forms with the investigators and their staff prior to study. The responsibilities of the Sponsor (or designee) include project compliance, data abstraction, data reporting, regulatory monitoring, problem resolution and prioritization, and coordination of the activities of the protocol study team and study-level medical monitoring. Accrual rates and extent and accuracy of evaluations and follow-up are to be monitored periodically throughout the study period. Potential problems will be brought to the attention of the study team for discussion and action.

Investigators are responsible for the completeness of patient records, the accuracy of entries on the case report forms, the adherence to the protocol and to Good Clinical Practice, the progress of enrollment, and also to ensure that study medication is being stored, dispensed and accounted for according to specifications. Monitoring standards require full verification for the presence of informed consent, adherence to the inclusion/exclusion criteria, documentation of serious adverse events and the recording of primary efficacy and safety variables. Additional checks of the consistency of the source data with the case report forms are performed according to the institutional and regulatory guidelines.

It is the responsibility of the Principal Investigator at each of the study centers to oversee the safety of the study at his/her site. This safety monitoring will include careful assessment and appropriate reporting of adverse events as noted above. Medical monitoring will include a regular assessment of the number and type of serious adverse events.

The data collected for this study will be entered into a secure database. Source documentation will be available to support the computerized patient record. Random-sample data quality and protocol compliance audits will be conducted by the Sponsor (or designee) remotely (fax) or in person to check the completeness of patient records, the accuracy of entries on the case report forms, the adherence to the protocol and to Good Clinical Practice. The investigator must give the monitor access to relevant hospital or clinical records, to confirm their

A study of brentuximab vedotin (SGN-35) in CD30-positive systemic mastocytosis with or without an associated hematological clonal non-mast cell lineage disease (AHNMD)

consistency with the case report form entries. No information in these records about the identity of the subjects will leave the study center.

8.2.3 Auditing procedures

A regulatory authority may wish to conduct an inspection (during the study or even after its completion). If an inspection is requested by a regulatory authority, the investigator must inform Seattle Genetics immediately that this request has been made.

Seattle Genetics Good Clinical Practice Quality Assurance Unit may request to conduct an audit of clinical research activities to evaluate compliance with the principles of Good Clinical Practice.

8.2.4 Handling of study medication

All study medication will be supplied to the principal investigator by Seattle Genetics. Drug supplies must be kept in an appropriate, secure area (eg, locked cabinet) and stored according to the conditions specified on the drug labels. The investigator must maintain an accurate record of the shipment and dispensing of study drug in a drug accountability ledger, a copy of which must be given to Seattle Genetics at the end of the study. An accurate record of the date and amount of study drug dispensed to each subject must be available for inspection at any time.

All drug supplies are to be used only for this protocol and not for any other purpose. The investigator must not destroy any drug labels, or any partly-used or unused drug supply. At the conclusion of the study, and, as appropriate during the course of the study, the investigator will return all used and unused drug containers, drug labels and a copy of the completed drug disposition form to Seattle Genetics.

8.3 Ethics and Good Clinical Practice

This study must be carried out in compliance with the protocol and the principles of Good Clinical Practice, as described in standard operating procedures and:

1. ICH Harmonized Tripartite Guidelines for Good Clinical Practice 1996.
Directive 91/507/EEC, The Rules Governing Medicinal Products in the European Community.
2. US 21 Code of Federal Regulations dealing with clinical studies (including parts 50 and 56 concerning informed consent and IRB regulations).

A study of brentuximab vedotin (SGN-35) in CD30-positive systemic mastocytosis with or without an associated hematological clonal non-mast cell lineage disease (AHNMD)

3. Declaration of Helsinki and amendments, concerning medical research in humans (Recommendations Guiding Physicians in Biomedical Research Involving Human Subjects). The investigator agrees when signing the protocol to adhere to the instructions and procedures described in it and thereby to adhere to the principles of Good Clinical Practice that it conforms to.

8.3.1 Institutional Review Board/Independent Ethics Committee

Before implementing this study, the protocol, the proposed informed consent form and other information to subjects, must be reviewed by a properly constituted Institutional Review Board/Independent Ethics Committee/Research Ethics Board (IRB/IEC/REB). A signed and dated statement that the protocol and informed consent have been approved by the IRB/IEC/REB must be given to Seattle Genetics before study initiation. The name and occupation of the chairman and the members of the IRB/IEC/REB must be supplied to Seattle Genetics. Any amendments to the protocol, other than administrative ones, must be approved by this committee.

8.3.2 Informed consent

Patients will be required to sign a statement of informed consent which meets the requirements of the code of Federal Regulations (Federal Register Vol. 46, No. 17, Jan. 27, 1981, part 50) and the IRB of this center. The medical record should include a statement that written informed consent was obtained (and document in the record the date written consent was obtained before) and the patient is enrolled in the study.

The informed consent form is considered to be part of the protocol, and must be submitted by the investigator with it for IRB/IEC/REB approval.

Consent Process

The investigator must explain to each subject (or legally authorized representative) the nature of the study, its purpose, the procedures involved, the expected duration, the potential risks and benefits involved and any discomfort it may entail. Each subject must be informed that participation in the study is voluntary and that he/she may withdraw from the study at any time and that withdrawal of consent will not affect his/her subsequent medical treatment or relationship with the treating physician. The discussion will review the alternatives available, why the risks are reasonable in relation to the anticipated benefits, incentives, costs that will or may be incurred as a result of participation in the study, as will the efforts to maintain the confidentiality will also be discussed.

This informed consent should be given by means of a standard written statement, written in non-technical language. The subject should read and consider the statement before signing and dating it, and should be given a copy of the signed document. If the subject cannot read or sign the documents, oral presentation may be made or signature given by the subject's legally appointed representative, if witnessed by a person not involved in the study, mentioning that the patient could not read or sign the documents. No patient can enter the study before his/her informed consent has been obtained.

A copy of the signed original consent form will be given to the patient.

References

- Akin C, Metcalfe DD (2004). Systemic Mastocytosis. *Annu Rev Med*; 55: 419-432.
- Butterfield JH (1998). Response of severe systemic mastocytosis to interferon-alpha. *Br J Dermatol*. 138:489-495.

APPENDIX A

Performance Status Criteria

ECOG Performance Status Scale		Karnovsky Performance Scale	
Grade	Descriptions	Percent	Description
0	Normal activity. Fully active, able to carry on all pre-disease performance without restriction.	100	Normal, no complaints, no evidence of disease.
		90	Able to carry on normal activity; minor signs or symptoms of disease.
1	Symptoms, but ambulatory. Restricted in physically strenuous activity, but ambulatory and able to carry out work of a light or sedentary nature (eg, light housework, office work).	80	Normal activity with effort; some signs or symptoms of disease.
		70	Cares for self, unable to carry on normal activity or to do active work.
2	In bed <50% of the time. Ambulatory and capable of all self-care, but unable to carry out any work activities. Up and about more than 50% of waking hours.	60	Requires occasional assistance, but is able to care for most of his/her needs.
		50	Requires considerable assistance and frequent medical care.
3	In bed >50% of the time. Capable of only limited self-care, confined to bed or chair more than 50% of waking hours.	40	Disabled, requires special care and assistance.
		30	Severely disabled, hospitalization indicated.
4	100% bedridden. Completely disabled. Cannot carry on any self-care. Totally confined to bed or chair.	20	Very sick, hospitalization indicated. Death not imminent.
		10	Moribund, fatal processes progressing rapidly.
5	Dead.	0	Dead.

APPENDIX B

Criteria to Diagnose Systemic Mastocytosis (SM Criteria)

Major criterion	Multifocal dense infiltrates of mast cells (>15 mast cells in aggregates) in bone marrow biopsies and/or in sections of other extracutaneous organ(s)
Minor criteria	
a. >25% of all mast cells are atypical cells (type I or type II) On bone marrow smears or are spindle-shaped in mast cell Infiltrates detected on sections of visceral organsb. c-kit point mutation at codon 816 in the bone marrow or another extracutaneous organc. Mast cells in bone marrow or blood or another extracutaneous organ express CD2 or/and CD25d. Baseline serum tryptase concentration > 20 ng/ml (in the case of an unrelated myeloid neoplasm, (d) is not valid as an SM criterion)

If at least one major and one minor or three minor criteria are fulfilled, then the diagnosis is systemic Mastocytosis=SM.

A study of brentuximab vedotin (SGN-35) in CD30-positive systemic mastocytosis with or without an associated hematological clonal non-mast cell lineage disease (AHNMD)

APPENDIX C

Diagnostic Criteria for Aggressive Systemic Mastocytosis and Mast Cell Leukemia

Aggressive Systemic Mastocytosis

Meets criteria for SM

One or more “C” findings

No associated clonal hematologic malignancy/disorder (AHNMD)*

No evidence of mast cell leukemia

*Patients with aggressive systemic mastocytosis who also are found to have an AHNMD are eligible for this protocol

Mast Cell Leukemia

Meets criteria for SM

Biopsy shows a diffuse infiltration, usually interstitial pattern, by atypical, immature mast cells

Bone marrow aspirate smears show 20% or more mast cells

Mast cells account for 10% or more of peripheral blood white cells

NOTE: Patients may also be enrolled if mast cells account for <10% of the peripheral blood white blood cells; such patients are considered to be in the pre-phase of mast cell leukemia and are referred to as “aleukemic mast cell leukemia.”

APPENDIX D

Mediator Drugs to Ameliorate Symptoms Related to Systemic Mastocytosis*

Symptom	Step	Drug(s) to be considered	
Pruritis, flushing	1	H1 + H2-histamine receptor antagonists	
	2	Ketotifen, topical glucocorticoids	
	3	PUVA	
Cardiovascular symptoms Recurrent hypotension and tachycardia	1	H1 + H2-histamine receptor antagonists	
	2	Glucocorticoids**	
	3	Aspirin (in selected cases)	
Recurrent shock	1	H1 + H2-histamine receptor antagonists + epinephrine on demand (self injected)	
	2	Oral glucocorticoids** + epinephrine on demand (self injected)	
	3	Aspirin (in selected cases) + epinephrine on demand	
GI tract Peptic ulcer disease	1	H2-histamine receptor antagonists	
	2	Proton-pump inhibitors + H2 blockers	
	Diarrhea, abdominal pain, cramping, nausea/vomiting	1	H1 + H2-histamine receptor antagonists
		2	Oral cromolyn sodium
	3	Consider trial with leukotriene antagonists	
	4	Short-term glucocorticoids**	
Skeletal system Bone pain	1	Analgesias, aspirin-like drugs (if tolerable) Also consider radiation for severe pain	
Osteopenia, diffuse osteoporosis	1	Vitamin D + calcium or estrogen/ testosterone on demand	
	2	Bisphosphonates	
Neurologic symptoms	1	H1 + H2-histamine receptor antagonists	
	2	Oral cromolyn sodium	

*From Valent *et al.* Br J Haematol. 2003; 122: 695-717.

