2.3.2 Secondary Efficacy Endpoints

- Immunohistochemical expression of CD30 on neoplastic mast cells in core biopsy samples or by flow before SGN-35 treatment and after 4 and 8 cycles of therapy
- Total symptom score and QOL score using a modified Myeloproliferative Neoplasm Symptom Assessment Form (MPN-SAF)
- Duration of response (DoR) is defined as the time from first onset of confirmed response to the date of first documented and confirmed progression or death due to ASM/MCL. Time to response (TTR) is defined as the time from start of treatment until the date of onset of a confirmed response
- Progression-free survival (PFS) is defined as the time from start of treatment to the date of the first documented and confirmed progression or death or institution of new therapy

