4.4 Concomitant therapy

In general, the use of any concomitant medication/therapies deemed necessary for patient supportive care and safety are permitted provided they are documented in the patient records. A list of medications which may be used to treat mediator-related symptoms are listed in **Appendix D**. All medications taken within 30 days of the first dose of study drug and all concomitant medications/therapies must be recorded on the Concomitant/Non-Drug Therapy CRF.

Women will avoid breast-feeding, and all women of childbearing potential will be required to use barrier contraception for the duration of the study and for 3 months post study.

Other anti-cancer agents including chemotherapy, radiation therapy, or biologic response modifiers are not permitted during the study. No other investigational drug is allowed during the study. Hematopoietic growth factors are not permitted during study (except G-CSF for neutropenic fever). Prophylaxis may be used for the prevention of nausea and vomiting and is at the discretion of the investigator.

Other anti-cancer agents including chemotherapy, radiation therapy, or biologic response modifiers are not permitted during the study. The exception is the use of hydroxyurea to control a proliferative leukocyte count related to a concurrent myeloid neoplasm (eg, CMML, or other MDS/MPN, or MPN associated with advanced SM). No other investigational drug is allowed during the study. Hematopoietic growth factors are not permitted during the study.

(except G-CSF for neutropenic fever). The exception is the use of erythropoiesis stimulating agents (with or without IV iron) in patients who are Jehovah's witnesses and for religious reasons are not permitted to undergo treatment with blood products. Prophylaxis may be used for the prevention of nausea and vomiting and is at the discretion of the investigator.

During treatment with SGN-35, glucocorticoids can be used in the event of appropriate need, as outlined in **Appendix D**, "Mediator Drugs to Ameliorate Symptoms Related to Systemic Mastocytosis."

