7.6.5 Progression-free survival (PFS) and overall survival

Progression-free survival (PFS) is defined as the time from the date of start of treatment until the date of first documented confirmed disease progression or death or institution of new therapy. If a patient did not progress or die due to any cause at the time of the analyses, PFS will be censored at the date of the last adequate response assessment. Kaplan-Meier product-limit estimates will be used to summarize PFS. For overall survival, patients will be contacted every 6 months until the study closure or death.

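### The PFS censoring sentence in 7.6.5 omits new therapy, which 2.3.2 and 7.6.5 define as a PFS event; whether palliative radiation is allowed, and counts as new therapy, also needs a line

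*Combined protocol and SAP*

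**What the plan says.** **PFS.** Section 2.3.2 measures PFS from start of treatment "to the date of the first documented and confirmed progression or death or institution of new therapy". Section 7.6.5 repeats this: "until the date of first documented confirmed disease progression or death or institution of new therapy". Its next sentence gives the censoring rule: "If a patient did not progress or die due to any cause at the time of the analyses, PFS will be censored", with the censoring date set at the last adequate response assessment. PFS is then summarised by Kaplan-Meier.

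**Radiation.** Section 4.4 opens by saying that "the use of any concomitant medication/therapies deemed necessary for patient supportive care and safety are permitted". Two near-duplicate paragraphs then state: "Other anti-cancer agents including chemotherapy, radiation therapy, or biologic response modifiers are not permitted during the study". The second adds an exception to that bar: "The exception is the use of hydroxyurea to control a proliferative leukocyte count related to a concurrent myeloid neoplasm". For mediator-related symptoms, 4.4 points to Appendix D: "A list of medications which may be used to treat mediator-related symptoms are listed in" that appendix. Under bone pain, step 1, Appendix D adds: "Also consider radiation for severe pain".

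**The concern.** The definition of PFS has three events, but the censoring condition names only two. A patient who starts new therapy without progression or death has a defined event, yet also meets the stated condition for censoring. An analyst who follows the definition records an event at the start of therapy. One who follows the censoring sentence discards that event and goes back to the last adequate assessment. The second choice can only raise the PFS curve.

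The protocol leaves room for such patients. Section 7.5 counts stable disease as non-response. Section 4.6.1 gives non-responders one visit about 30 days after end of treatment, followed by survival contact every 6 months. Section 4.3 lists reasons for stopping, such as adverse events and unsatisfactory effect, that do not require progression.

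Radiation connects to this in one place. If a patient receives it for bone pain, the plan does not say whether that is permitted supportive care, or whether it is new therapy for PFS.

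**Working it through.** **1. Compare events with censoring conditions.**

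| Endpoint | Events in the definition | Censored if none of these occurred |
|---|---|---|
| DoR (7.6.4) | progression; death due to ASM or MCL | progression; death due to ASM or MCL |
| PFS (2.3.2, 7.6.5) | progression; death; new therapy | progression; death |

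The DoR condition covers all of its events. The PFS condition lacks one of three.

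**2. Size of the effect.** The plan gives no PFS figure to reproduce and no frequency of new therapy without progression. Let *n* be the number of patients, *d* the earlier progressions or deaths, and *m* the patients who later start new therapy without either. *m* is an assumption and may be zero. Assume no other censoring and no progression or death between the starts. Just after the last start:

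- New therapy as an event: S = (n − d − m)/n.
- Censored, last adequate assessment after all *d* events: S = (n − d)/n. Gap = m/n.
- Censored, last adequate assessment before all *d* events: S = (n − m − d)/(n − m). Gap = (m/n) × [1 − d/(n − m)], which is below m/n whenever d > 0.

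Example with n = 11, d = 3, m = 1:

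- Event: 7/11 = 63.6%.
- Censored after all three progressions: 8/11 = 72.7%, gap 9.1 points.
- Censored after two: 10/11 × 9/10 × 7/8 = 71.6%, gap 8.0 points.
- Censored after one: 10/11 × 8/9 × 7/8 = 70.7%, gap 7.1 points.
- Censored before all three: 7/10 = 70.0%, gap 6.4 points.

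Range of the gap in percentage points with d = 3, from last assessments before all three events to last assessments after all three:

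| m | n = 11 | n = 26 |
|---|---|---|
| 0 | 0 | 0 |
| 1 | 6.4 to 9.1 | 3.4 to 3.8 |
| 2 | 12.1 to 18.2 | 6.7 to 7.7 |
| 3 | 17.0 to 27.3 | 10.0 to 11.5 |

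The n = 26 column applies only if the second stage opens.

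**3. Primary analysis.** The Simon design in 7.8 uses response counts only: continue with at least 2 of 11, success with at least 5 of 26. Summing Binomial(11, p) over x ≥ 2 times P(Binomial(15, p) ≥ 5 − x) gives 0.0865 at p = 10% (stated alpha 8.7%) and 0.852 at p = 30% (stated power 85%). Early stopping is 0.697 and 0.113 (stated 70% and 11%). All four reproduce, and none depends on PFS or on the radiation wording.

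**The case against.** **On PFS.** Censoring ordinarily applies only to patients without an event. The definition stands directly before the censoring sentence and agrees with 2.3.2, so most statisticians would code new therapy as an event and read the short condition as an omission. That is the likely intent, and it keeps the point minor. It does not make the rule correct: the sentence states its own condition in mandatory terms, and a programmer who follows it would code the opposite.

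The scenario is also narrow. After the end-of-study visit the schedule lists only survival follow-up for non-responders, so some later starts of therapy may never be recorded. This stands as a limit: rewording settles how known starts are coded but does not create missing data.

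**On radiation.** A reader might infer that 4.4 bars radiation for any purpose, so that Appendix D contradicts it outright and should lose the remark. The documents do not support this. Section 4.4 names radiation as a member of the class of anti-cancer agents, opens by allowing supportive-care therapies, and cites Appendix D as a list of what may be used. A consistent reading exists: radiation against the disease is barred, and radiation for pain is supportive care. What remains is that no sentence says so, and the exception attached to the bar concerns hydroxyurea only, so sites could differ in good faith.

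**Conclusion.** The 7.6.5 censoring sentence is wrong as written, and the issue is minor. Read literally, it turns an event defined in two places into a censored observation. With one affected patient among 11 and three earlier progressions, the Kaplan-Meier estimate differs by 6.4 to 9.1 points, depending on when that patient's last adequate assessment falls. A reader might take m/n as the gap in general. It is the upper end, reached only when the last adequate assessment follows all earlier events, because 7.6.5 censors at that assessment and not at the start of new therapy.

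The size rests on an assumed number of patients, possibly zero, and on no other censoring. PFS is a descriptive secondary endpoint with no test or decision rule. Nothing here bears on the primary response rate or the go/no-go rules.

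The radiation wording is a secondary clarification, not a demonstrated contradiction.

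**What to change.** 1. In 7.6.5, extend the censoring condition to *did not progress, die due to any cause, or start new therapy*, and leave the rest of the sentence as it is. This is one phrase, with no added patients or procedures, and should be settled before PFS is analysed.
2. In 4.4, state whether palliative radiation for severe bone pain is allowed as supportive care. In 7.6.5, state whether it counts as new therapy. This takes one sentence in each place.

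Deleting the Appendix D remark should not be the default. It would remove a pain-relief option, which is a clinical decision for the sponsor, and under 8.3.1 a non-administrative amendment needs ethics committee approval.
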